Objective 4 (OUTCOMES): Improve and sustain **case management** of PPH and newborn resuscitation during observations of care, as measured by a) percent of women with undelivered placenta after 30 minutes who are

treated with oxytocin, and b) percent PPH cases that receive repeated dose of oxytocin or misoprostol, c) percent of newborns not breathing at birth who are breathing or being ventilated with bag & mask at one minute.

Objective 5 (IMPACT): Reduce over time: a) the percent of facility-based deliveries who experience PPH; b) the PPH-related case fatality rate, and c) the perinatal death rate (the fresh stillbirth rate and early newborn mortality rate at 24 hours or prior to discharge)¹.

Prior to presenting the hypotheses, we describe briefly below the three study arms and three time points of data collection. More description is provided in the Study Procedures section. (See Figure 1, page 11)

Table 1. Brief Description of Three Study Arms/Groups

Arm	Short Name	Component 1	Component 2	Component 3
		Training onsite (BAB, HBB) of providers, simulators left at facility	Peer Practice Coordinator (PPC) is trained and expected to hold weekly onsite practice sessions with providers	Mobile messages remind all trained providers to practice scenarios; and PPC has weekly mobile support from district trainer
1	Training-only	Yes	No	No
2	Partial Package	Yes	Yes	No
3	Full Package	Yes	Yes	Yes

Hypotheses

Overall Hypothesis: The partial package intervention (one-time, onsite training of providers, combined with low-dose, high-frequency peer-led practice sessions) and the full-package intervention (adding reminders and mobile support) will lead to significant gains in provider competencies (between immediately post-intervention to midline) and provider performance of key interventions *BAB* and *in HBB*, which are both maintained once the active intervention ceases.

Specific Hypotheses:

In BAB and in HBB related to the primary outcomes (see Section 4b5):

1. Provider competencies and performance will not decline (i.e. will be non-inferior) between midline and endline in the *full* package group.
2. Provider competencies and performance will not decline (i.e. will be non-inferior) between midline and endline in the *partial* package group.
3. At endline, the provider competency level and the performance level of the *partial* package group will be significantly higher than those of the training-only group.

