- (a) Pre- and post-training, providers will be assessed on knowledge and OSCE competency tests. There will be separate one-day trainings for BAB & HBB spaced 2 months apart.
- (b) At midline and endline providers will be given BAB and HBB knowledge tests and OSCE skills tests. Facility readiness assessments will also occur at these time points.
- (c) The number of providers in this table is taken from the ACTUAL number of providers that we are aware exist in the Eastern and Western region that attend births. All providers are invited to participate in the intervention and may be assessed.

Direct Clinical Observation: Number of births (women and newborns) to be observed

We specify the sample size of number of births to observe below. The outcome variable is: the percentage of women who **received oxytocin** in correct dose immediately after vaginal birth in three study arms. The hypothesized levels of this variable at each time point are presented below:

Table 4. Hypothesized levels of “percent of women who **received oxytocin** in correct dose “within 1 minute of vaginal birth” in three study arms

Study Arm	Baseline	Midline	Endline
Full	50% (a)	75%	70%
Partial	50%	65%	60%
Training-only	50%	55%	50%

Note:

- (a) A study carried out in 2007 (POPPHI, 2007) found that **20%** of women delivering at health facilities in Uganda received an oxytocin injection between birth and the delivery of the placenta. However, given the small sample size (n=259 births observed) and the fact that the situation may have improved (as it has in many countries), we have conservatively estimated baseline coverage of oxytocin use to be **50%**.

Table 5. Number of **births** to observe (women in labor and delivery)

Study Arm	Baseline	Midline	Endline	Total births
Full Intervention Group (expected: 50% at baseline to 75% at midline to 70% at endline)	189 67 to compare baseline-midline	378 (a) for midline-endline comparison 99, midline-only comparison 67 to compare baseline-midline	378 (a) for midline-endline comparison 189 endline-only (b)	1134
Partial Intervention Group (expected: 50% at baseline to 65% at midline to 60% at endline)	189 to compare baseline-midline	189 , to compare baseline-midline 99, midline-only comparison	189 , endline-only comparison (b)	567
Training-only Group (expected: 50% baseline to 55% at midline to 50% at endline)	189	189 , midline-only comparison	189 , endline-only comparison (b)	567
Grand Total	567	756	756	2079

Notes

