- (a) The number of **378 births** is recommended for each time point in the full package group only. N=378 is based on calculations for midline and at endline is based on a (within-group) non-inferiority calculation in the intervention group. We set the number of health facilities at 54 (9 facilities on average per district * 3 districts * each of 2 regions). This sample size will achieve 80% power to detect a non-inferiority margin difference between the group proportions of providing oxytocin of -0.1000. As shown in the previous table, the percent of deliveries with oxytocin provision at midline (post-intervention) is hypothesized to be 70% in Full group. We assume intra-class correlation (ICC) of 0.005 and significance level of the test is 0.0250.
- (b) The number of **189 births** in each group at endline (only) is based on the following assumptions: This is a two-sample comparison of proportions. We aim to detect a 15% point difference at endline between an intervention group and the training-only group. Training-only group value set at 50%, as this is most conservative. Intervention group value set at 65%. Power is set at 80%. ICC is set at 0.01.
- (c) To avoid oversampling, and to compensate for different caseloads at different facilities, the study team will be given a target number of births to observe and they will stop when they reach this target. There will be no overlap in the number of women observed, because different women will be observed at different time points.

Service Statistic Data Abstraction

There is no sample size calculation for analysis of service delivery statistics because baseline data from the study health facilities are not available.

Qualitative Data: Focus Group Discussions and In-depth Interviews

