2. Provider competencies and performance will not decline (i.e. will be non-inferior) between midline and endline in the *partial* package group.
3. At endline, the provider competency level and the performance level of the *partial* package group will be significantly higher than those of the training-only group.
4. At endline, the provider competency level and the performance level of the *full* package group will be significantly higher than those of the training-only group.

Hypotheses 1 and 2:

This is a non-inferiority analysis. Two-sided 90% confidence intervals (CI) for the difference in average knowledge and competence scores between midline and endline will be constructed, separately for full and partial package groups. Non-inferiority will be determined comparing the upper bound of the 90%CI for the difference between the 2 time points to the pre-specified non-inferiority margin of 0.06 (22). If the CI's upper bound is less than the predefined margin, then we are able to claim non-inferiority of the endline knowledge scores to the midline knowledge at a 0.05 level of significance.

We will first examine the differences in sample means of knowledge scores between midline and endline not adjusted for any potential confounding variables. The confidence intervals for the knowledge scores will be calculated using generalized linear models with knowledge and competencies as the dependent variables and time variable (endline vs. midline) as the primary independent variables. To account for repeated observations within providers at midline vs. endline, we will use robust Huber/White estimate of variance implemented in STATA through 'vce' (cluster) option. In addition, adjusted 90% CI for the difference in means will be constructed by adding provider- and facility-level factors in the model.

Hypotheses 3 and 4:

We will examine differences in competencies and performance at endline between the 3 study groups using generalized linear models. The dependent variables in these models will be:

- 1) knowledge and competency scores,
- 2) proportion of women who received **oxytocin** (at correct dosage) within one minute of a vaginal birth,
- 3) proportion of women whose placenta was inspected within 16 minutes, and
- 4) proportion of newborn checked for breathing within 1 minute.

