The primary independent variable will be the study group represented as 2 indicator variables for full and partial training package with training-only as the reference group. For these hypotheses, we will only use endline data. Additional variables, related to provider- and facility characteristics predictive of these outcomes, such as cadre, number of years of provider's experience, and number of prior births attended in last 90 days, will be also included in the model. Analysis of residuals will inform whether the assumptions of the generalized linear model, such as normality and homoscedasticity of residuals as well as linear fit, are satisfied.

Additional analyses will include:

1. At baseline, midline and endline we will collect data from **all study facilities** consisting of service delivery statistics, and facility inventory. These data will be analyzed using population-average marginal generalized linear models estimated using generalized estimating equations (GEE) with exchangeable working correlation structure to account for repeated observations within facilities. The dependent variable will be service delivery statistics. The independent variables will include time (represented as 2 indicator variables for midline and endline with baseline as the reference group), study group (represented as 2 indicator variables for full and partial training groups with training-only as the reference group), and interaction terms (study group by time). The interaction terms will be examined to assess whether there are differences between study groups that change significantly over time.
2. Providers who are trained will keep **logs of their practice sessions**. This is process evaluation data. These data (for example on number of times a scenario is practiced) will be compared across the three study groups using generalized linear models with Poisson or Negative Binomial distribution for the outcome.
3. **Routinely collected data from health facility registers** (recorded daily but aggregated monthly) on services provided to clients and health outcomes (discharge, or deaths and stillbirths) will be analyzed using longitudinal data analysis to account for repeated observations at each facility. This will be for population-averaged marginal generalized linear models using generalized estimating equations (GEE) and exchangeable working correlation structure.

Qualitative Analysis

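### The overall hypothesis claims a gain that is then maintained, but Section 4b5 specifies no analysis of the gain phase, and the 567 baseline births enter none of the four hypothesis tests

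*Combined protocol and SAP*

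**What the plan says.** Section 1 (Overall Hypothesis) expects significant gains in provider competencies, "between immediately post-intervention to midline", and in provider performance, "which are both maintained once the active intervention ceases". Section 4b5 lists change in knowledge and competence as a secondary outcome.

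Table 5 in Section 3c plans 567 baseline births and attaches purposes to its sample sizes. The partial arm has "189 to compare baseline-midline", the full arm has 67 for the same purpose, and both carry "99, midline-only comparison". Training-only has 189 for the midline-only comparison.

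For Hypotheses 1 and 2, Section 4b5 builds confidence intervals "for the difference in average knowledge and competence scores between midline and endline", with time coded as endline against midline. For Hypotheses 3 and 4 it states "For these hypotheses, we will only use endline data". Among the additional analyses, one GEE model includes baseline as a time level and a group-by-time interaction, but its outcome is service delivery statistics.

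On provider scores, Table 3 note (a) says: "Pre- and post-training, providers will be assessed on knowledge and OSCE competency tests". Section 4b2 adds tests at the baseline visit, and Section 3d says providers are linked over time.

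**The concern.** Non-inferiority from midline to endline shows only that a level did not fall. An arm at 50% at baseline, midline and endline would meet it. Without a test of the rise, the first half of the overall hypothesis rests on whatever baseline comparison is chosen after the data are seen. Section 4b10 says the results will inform recommendations to government on scale-up, so this matters.

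The starting point of the competency gain is also undefined. Table 5 note (a) describes the oxytocin rate "at midline (post-intervention"). If midline is itself post-intervention, a gain from post-intervention to midline spans no time. The natural alternative is the post-training test.

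For the score outcomes of Hypotheses 3 and 4, the endline-only rule sets aside a baseline measure that is collected and linkable.

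**Working it through.** **1. Match each planned comparison to an analysis of observed births or scores.**

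| Comparison | Sized in Table 5 | Analysis in Section 4b5 |
|---|---|---|
| Baseline to midline, performance | 67 full, 189 partial | none |
| Post-training to midline, scores | not sized | none |
| Midline between arms | 99 full, 99 partial, 189 training-only | none |
| Midline to endline (H1, H2) | 378 full | contrast stated; method written for scores |
| Endline between arms (H3, H4) | 189 per arm | endline data only |

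Baseline births: 3 × 189 = 567, and 567/2079 = 27.3%. None enters H1 to H4.

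**2. Reproduce the plan's sizes.** Two-sample proportions, two-sided 0.05 (my assumption; note (b) gives no alpha), 80% power, continuity correction, ICC 0.01, inflated by n = n0(1 − ICC)/(1 − n0·ICC/k), with k = 54 facilities (note (a)).
- 50% vs 65%: n0 = 183; 183 × 0.99/(1 − 1.83/54) = 187.5 (189.0 with k = 133/3). Plan: 189.
- 50% vs 75%: n0 = 66, giving 66.1. Plan: 67.
- 75% vs 55%: n0 = 98, giving 98.8. Plan: 99.

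So 99 fits full against training-only at midline. Partial against training-only at midline (65% vs 55%) needs 376 per arm before correction or clustering. At 189 per arm, z = [0.10 − 1.96√(2 × 0.60 × 0.40/189)]/√[(0.2475 + 0.2275)/189] = (0.10 − 0.0988)/0.0501 = 0.02, which is about 51% power.

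**3. Power for the baseline-to-midline oxytocin gain.** Rates are from Table 4. The district draw in Section 3 gives 12 districts, four per arm, so 189/4 = 47.25 births per district and round (378/4 = 94.5 for full at midline). With ρ the between-round correlation of district rates:

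SE² = [2·ICC·0.25·(1 − ρ) + p0q0/47.25 + p1q1/n1]/4

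The plan's ICCs (0.005 and 0.01) have facilities as clusters; using 0.01 for districts is an assumption. Power is from the noncentral t, with 9 df if variance is pooled over 12 districts, or 3 df on the arm's own four.

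| Arm, gain | ρ | SE | 9 df | 3 df |
|---|---|---|---|---|
| Partial, 15 points | 1 | 0.0503 | 76% | 53% |
| Partial, 15 points | 0 | 0.0615 | 59% | 39% |
| Full, 25 points | 1 | 0.0426 | >99% | 96% |
| Full, 25 points | 0 | 0.0554 | 98% | 84% |

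For partial with ρ = 0: (0.0050 + 0.0053 + 0.0048)/4 = 0.00378, whose root is 0.0615. Ignoring clustering, the partial figure is 84% to 85%. On 9 df it is 66% to 76% at ICC 0.005 and 30% to 76% at an assumed 0.05.

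The difference in gain from training-only (10 points partial, 20 points full, since Table 4 expects training-only to rise 5) has 18% to 24% and 57% to 76% power at ICC 0.01, 9 df.

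**4. Precision from adjusting scores.** With 651/12 ≈ 54 providers per district and pre/post correlation r, the fall in standard error is 1 − √{[ICC + (1 − ICC)(1 − r²)/54]/[ICC + (1 − ICC)/54]}. For assumed r = 0.3, 0.5, 0.7 this is 3%, 8%, 17% at district ICC 0.01 and 1%, 3%, 7% at 0.05.

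**The case against.** The plan pairs H1 and H2 with H3 and H4. An arm that stayed low should not beat training-only at endline, and a contrast between arms drawn by lot is better evidence than a within-arm rise. Every arm is trained, the investigators work on oxytocin supply, and Section 8 concedes that observation may change behaviour. This largely stands, and is why the training-only change must sit beside any within-arm gain. It does not close the gap: a flat partial arm could still meet H2 and H3 if training-only fell, and neither hypothesis estimates the gain that Section 1 claims.

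The data analysis plan calls itself brief, the covariate list for H3 and H4 is illustrative, Section 3c announces a correlation analysis involving observed performance, and Section 3d a longitudinal linkage of providers. These narrow the gap, but none is a test of gain.

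Four stronger readings are tempting and not supported:
- That H3 and H4 are biased for want of a baseline. Districts are drawn by lot, and these hypotheses ask only about endline level.
- That baseline data are used nowhere. The service-statistics model uses baseline.
- That competency may be called maintained only after a rise from the post-training test. Section 4b10 asks about improvement or maintenance, so an arm that held its post-training score has answered the question.
- That oxytocin should also be adjusted for district baseline rates. In a simulation on 12 district means at ICC 0.005 and 0.01, this widened the 95% interval half-width by 0.2 to 1.1 points.

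**Conclusion.** The gap is real and lies in what Section 4b5 omits. The gain phase of the overall hypothesis has no specified analysis, although Table 5 sizes one; 27% of the planned births enter none of the four tests; and H1 and H2 alone cannot support a claim of gain followed by maintenance. The four hypotheses can stay as worded, and H3 and H4 remain valid.

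The score adjustment is a smaller matter: a standard error about 1% to 17% lower, under assumed correlations of 0.3 to 0.7 and district ICCs of 0.01 to 0.05. The power figures rest on Table 4's rates, four districts per arm and an assumed district ICC, which the plan does not give. Joint power for gain and non-inferiority was not calculated; it cannot exceed the power for the gain.

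**What to change.** 1. Prespecify a baseline-to-midline analysis of observed performance in the full and partial arms, with district-level clustering and a small-sample correction. Show the training-only change beside it and report the between-arm difference in change with a confidence interval. Claim gain followed by maintenance for performance only where both the gain and non-inferiority are shown. Requiring both needs no alpha split within an arm. The non-inferiority method must also be written for observed performance, since it is now described only for scores.
2. Define the post-intervention starting point in Section 1, and report the post-training-to-midline change in competency scores with a confidence interval. Do not make it a condition for calling competency maintained.
3. Specify the midline-only arm comparison or delete it from Table 5. If kept, state that 99 fits full against training-only and that partial against training-only has about 51% power before clustering.
4. For knowledge and competency scores in H3 and H4, replace the endline-only rule with endline score adjusted for the provider's pre-training score, in a model that keeps providers who lack one. For HBB, prefer the baseline-visit score: the HBB training day comes eight weeks after the first training, when peer practice is already under way in two arms.

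The cost is plan wording and extra analysis, with no new data. The claim of gain plus maintenance becomes harder to make, mainly in the partial arm.

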Step 2. We surveyed the country with guidance from Ministry of Health publications and consultations, and excluded districts that have or recently had an active maternal health or newborn health intervention, as this would dilute the effect of our intervention or result in high levels of quality of birth care at baseline, with little room for improvement.

Step 3 We combined Western and Southwest Regions into one group and Eastern and East Central Region into a second group in order to consolidate as Western had only 4 possible districts and East Central had only 3.

Step 4. We examined the a) number of facilities by type in each district and b) caseload of births in one year (July 2012- June 2013) in each district, and calculated the average number of births per facility per day. We then selected all districts within the two groups that had an average of > or = to one birth per facility per day. This resulted in 6 districts in the Eastern group and 6 in the Western group.

All public Level II, III, and IV facilities offering birthing services within a district will be included (range of 7-17 per district for a total of 133 facilities). In districts where there is no public hospital, we will include any Private Not for Profit hospital providing birthing services in that district where they exist. In all of these facilities, as mentioned in Section 3c, an estimated 1,300 providers will be included in the study.

District assignment to intervention arm:

In each region we will divide the six districts into two groups of three. Within the groups of three we will randomly choose a district name from a hat. For the district pulled we will draw a number card with a “1”, “2”, or “3” from a hat. Those numbers will correspond with the study arms outlined in Table 1 (page 2).

- Describe the study participants and the population from which they will be/were drawn. If you plan to include children, specify their ages and gender.

Study participants include any providers at selected facilities who provide birthing services to women and all women admitted to the labor ward for labor. (Table 2 presents the maximum number of study contacts per participant.

Table 2. By research objective, Participants (Sample and Population), Data Source, and Number of Contacts

Obj.	Study Participants (Sample & Population)	Data Source	Number of Study Contacts

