We will conduct a doer/non-doer analysis that will contrast providers and managers at facilities that adhere to low-dose/high-frequency practice recommendations with providers at facilities with few or no reported practice sessions. We will also analyze interviews with key stakeholders to identify their recommendations regarding program sustainability. Audio-recordings of focus group discussion and interviews will be transcribed and entered into Atlas.ti software. Data from close-ended questions will be entered into Microsoft Excel or Stata. Pre-determined and emergent codes will be developed, and content analysis will be conducted.

- 6) If human biospecimens (blood, urine, saliva, etc.) will be collected . N/A
- 7) Describe how **subjects** will be **screened for eligibility and assigned to** study/intervention and comparison/control groups.

All providers who attend births at the facilities will be invited to participate. All women who are in labor at the facility on the days of observation will be invited to participate (delivery and newborn care will be observed).

Criteria for being a PPC include: being an experienced skilled birth attendant and likely to remain at the facility during the study period (i.e. no imminent transfers).

- 8) Explain and justify whether there will be **blinding**.

Randomization or blinding of individual subjects is not feasible in this study because of the district-randomized design.

- 9) Explain and justify whether participants **will not receive routine care** or will have current therapy stopped.

Women in labor and delivery (participants) and their newborns will receive routine care as per Ugandan guidelines.

- 10) Explain and justify the use of a placebo or **non-treatment group**.

All study groups will receive the training on Bleeding after Birth and Helping Babies Breathe, and simulators (anatomic models) will be left behind at all facilities. The training-only (comparison) group will be encouraged to practice regularly but will receive no peer support intervention or SMS messages.

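### Arms are assigned by district, but the GEE models for service statistics allow for correlation only within facilities, so standard errors for arm contrasts are too small if facilities in a district are alike

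*Combined protocol and SAP*

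**What the plan says.** **Allocation.** Section 3 (Regional and District selection) ends with 12 districts: "This resulted in 6 districts in the Eastern group and 6 in the Western group". Under District assignment to intervention arm, the six districts of each region are split into two groups of three, and arms are drawn inside each group: "Within the groups of three we will randomly choose a district name from a hat". Each triplet supplies one district per arm, so there are four districts per arm. Section 4b8 explains the absence of blinding "because of the district-randomized design", although section 4b1 calls the study quasi-experimental. The facilities are nested in these districts: "range of 7-17 per district for a total of 133 facilities".

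**Analysis.** Section 4b5, Additional analyses, item 1 fits marginal GEE models to service delivery statistics with an "exchangeable working correlation structure to account for repeated observations within facilities". The terms are time, study group and their interaction, and "The interaction terms will be examined to assess whether there are differences between study groups that change significantly over time". Item 3 covers monthly register data on services, discharges, deaths and stillbirths. These "will be analyzed using longitudinal data analysis to account for repeated observations at each facility", again by GEE with an exchangeable structure. It lists no covariates.

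Neither item names a district cluster, a district effect, a region or triplet term, a variance estimator or a reference distribution. The only cluster-robust variance in section 4b5 is at provider level, for Hypotheses 1 and 2.

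**The concern.** The exposure varies over 12 units, but the model's independent unit is the facility. Anything that makes facilities in a district resemble each other, or move together over time, adds variance to an arm contrast that facility-level clustering does not see. With four districts per arm, one atypical district can look like an intervention effect.

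Items 1 and 3 are the only quantitative models stated for the outcomes of Objective 5 (PPH, PPH case fatality, perinatal death). Section 4b10 says the results will inform recommendations to government on scale-up, so overstated certainty about a difference between arms would matter.

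**Working it through.** **A figure to reproduce.** There is none. Section 3c says no sample size was calculated for the service statistics, and the plan gives no power or standard error for these models.

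**Inputs from the documents (section 3).** 133 facilities, 12 districts, three arms, 7 to 17 facilities per district. The mean is J = 133/12 = 11.1 facilities per district.

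**Assumed input.** The district ICC, ρ, is the share of between-facility variance that lies between districts. For a contrast at one time point it refers to facility means. For an arm-by-time interaction it refers to facility-level change. The ICCs in section 3c do not supply it: both concern observed births, the 0.005 goes with a count of health facilities, and the 0.01 has no level named.

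**Formulas.** Design effect DE = 1 + (J − 1)ρ. The standard error is understated by √DE. The true type I error of a nominal 5% test is 2[1 − Φ(1.96/√DE)].

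| ρ (assumed) | DE, J = 11.1 | SE factor | Type I error |
|---|---|---|---|
| 0 | 1.00 | 1.00 | 5.0% |
| 0.01 | 1.10 | 1.05 | 6.2% |
| 0.02 | 1.20 | 1.10 | 7.4% |
| 0.05 | 1.50 | 1.23 | 11.0% |
| 0.10 | 2.01 | 1.42 | 16.7% |

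At ρ = 0.05, moving J over the stated range of 7 to 17 gives factors of 1.14 to 1.34 and type I error of 8.6% to 14.4%.

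**Simulation of a two-arm contrast** (4 districts × 11 facilities per arm, 20,000 runs, no true effect):

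- Facility-level robust variance with a z reference rejects in 5.4%, 6.7%, 8.2%, 11.8% and 17.9% of runs at ρ = 0, 0.01, 0.02, 0.05 and 0.10. This is slightly above the formula.
- District-level robust variance, uncorrected and with a z reference, rejects in about 14% at every ρ, including 0. Four clusters per arm are too few for it.
- A t test on district means (4 + 4 − 2 = 6 df) rejects in about 5% throughout.

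**Simulation of the three-arm, three-time exchangeable GEE clustered on facility** (400 runs per row; residual SD 1, facility SD 1):

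| District SD | District-by-time SD | Endline interaction | Endline arm contrast |
|---|---|---|---|
| 0 | 0 | 4.8% | 5.5% |
| 0.32 | 0 | 6.3% | 11.0% |
| 0.32 | 0.32 | 17.8% | 18.5% |

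The second row shows a constant district effect largely cancelling from the interaction while still inflating the single-time contrast. The third row shows that district-by-time variation does not cancel.

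**Degrees of freedom at district level.** Arm only: 12 − 3 = 9. Arm and region: 12 − 3 − 1 = 8. Arm and triplet: 12 − 3 − 3 = 6.

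**Permutation counts**, taking each arm to be drawn once per triplet. For the three-arm global null there are (3!)⁴ = 6⁴ = 1,296 allocations. For one pair of arms there are 2⁴ = 16, so the smallest two-sided p is 2/16 = 0.125.

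**The case against.** The strongest reply has four parts.

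1. **Scope.** A reader might infer that the plan tests arm effects on mortality with too-small standard errors. The documents do not go that far. Only item 1 states arm terms, and its outcome is the general class of service statistics. Deaths and stillbirths are named in item 3, which lists no arm term. Objective 5 and the matching secondary outcome speak of change over time, and Hypotheses 1 to 4 concern only provider competency and performance. This stands: an arm contrast from item 3 is implied at most.

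2. **Omission or error.** The analysis plan calls itself brief, and items 1 and 3 do not state a variance estimator, so a district-level one could still be chosen. This stands only in part. The items do say which dependence they account for, and it is the facility. An analyst who follows them uses the wrong unit for arm contrasts.

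3. **Mechanism.** A reader might also infer that shared supplies, management and referral within a district are documented. They are not. Section 4b13 has each facility identify its own referral plan, supplies are to be secured with ministry officials, and the district trainer's weekly support applies to the full-package arm only. What the documents do show is that district authorities name some trainees and district officials help identify peer practice coordinators (section 6a). That makes positive correlation within districts plausible but gives it no size.

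4. **Size.** With no district ICC in the documents, the inflation could be nil, and item 1's interactions are immune to a constant district effect. This also stands, and it is why the range starts at zero.

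Finally, these are secondary models. The endline models for Hypotheses 3 and 4, which include the oxytocin primary outcome, state no clustering adjustment at all. That is the more serious gap, but closing it would leave items 1 and 3 as they are.

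**Conclusion.** The concern holds in a limited form. The unit of assignment is the district, and the stated GEE models account for dependence only within facilities. Standard errors for arm contrasts are therefore too small whenever facilities in a district are positively correlated. For item 1's interactions the correlation that counts is in change over time.

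The mismatch and its direction are firm; the size is not. Over the assumed ICC range of 0 to 0.10 with about 11 facilities per district, it runs from no effect to a standard error understated by a factor of 1.42 and about 17% false positives at a nominal 5%. At 0.01 the effect is slight (about 6%). The documents do not support a claim that the standard errors are certainly wrong by a known amount, or that item 3 as written tests arms. The point should be corrected before analysis, but it concerns additional analyses and not the primary outcomes.

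**What to change.** In section 4b5, Additional analyses, items 1 and 3:

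- State that district is the independent unit for every contrast between arms. In item 3, say whether an arm contrast is intended and, if so, list its terms.
- Prespecify a small-sample method. One option is an analysis of district-level summaries, or of district-level changes for the interactions, with a t reference. Another is GEE clustered on district with a bias-corrected variance and a t reference. Changing the cluster variable while keeping an uncorrected sandwich variance and a z reference is not sufficient.
- Say whether region or triplet is fitted, since the draw was made within them, and match the degrees of freedom: 9 with arm only, 8 with region, 6 with triplet.
- If a permutation test is wanted, use the 1,296 within-triplet allocations for the global three-arm null only. A pairwise version with 16 arrangements cannot reach p < 0.05.
- Add the same district-level accounting to the endline models for Hypotheses 3 and 4.

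The change is to analysis wording and code, with no new data collection. The price is wider confidence intervals and low power with four districts per arm. Fitting triplets costs a further three degrees of freedom (9 to 6).
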